5.2 Exclusion criteria

Participants meeting any of the following criteria are not eligible for inclusion in this study.

1. Severe concomitant non-CV disease that is expected to reduce life expectancy to less than 2 years at screening or baseline visit.
2. Participants on more than one other lipid-lowering drug on top of statin at screening visit.
3. Pre-existing diagnosis of homozygous familial hypercholesterolemia at screening or baseline visit.
4. Secondary hypercholesterolemia, e.g. hypothyroidism or nephrotic syndrome at screening or baseline visit.
5. Previous (within 90 days of screening), current or planned treatment with a monoclonal antibody (mAb) directed towards PCSK9 (e.g. evolocumab, alirocumab) at screening or baseline visit.
6. Previous exposure to inclisiran or any other non-mAb PCSK9 targeted therapy, either as an investigational or marketed drug within 2 years prior to screening or baseline visit.
7. Previous, current or planned treatment with LDL-apheresis at screening or baseline visit.
8. Participants with known intolerance to rosuvastatin at screening or baseline visit.
9. History of hypersensitivity to any of the study treatments, inclisiran or rosuvastatin, or its excipients or to drugs of similar chemical classes at screening or baseline visit.
10. Participants taking gemfibrozil at screening or baseline visit.
11. Liver and CK: (a) Active liver disease defined as any current infectious, neoplastic, or metabolic pathology of the liver or (b) unexplained alanine aminotransferase (ALT), aspartate aminotransferase (AST) elevation $>3\times$ ULN, or total bilirubin elevation $>2\times$ ULN (except for participants with Gilbert's syndrome), or (c) creatine kinase (CK) $>5\times$ ULN at screening or baseline visit.
12. Participant with severe renal impairment defined by $eGFR <30$ mL/min/1.73m² as calculated by the Modification in Diet in Renal Disease (MDRD) formula at screening or baseline visit.
13. Acute coronary syndrome, ischemic stroke or TIA, coronary revascularization or peripheral arterial revascularization procedure or amputation due to atherosclerotic disease <3 months prior to the screening or baseline visit.
14. Planned or expected cardiac, cerebrovascular or peripheral artery surgery or coronary revascularization within the study duration.
15. Heart failure New York Heart Association (NYHA) class IV at screening or baseline visit.
16. History of malignancy that required surgery (excluding local and wide-local excision), radiation therapy and/or systemic therapy (excluding systemic adjuvant therapies given to prevent cancer recurrence eg: hormone therapy for prostate or breast cancer) during the 3 years prior to screening or baseline visit.
17. Participant with myopathy at screening or baseline visit.
18. Participant receiving concomitant ciclosporin at screening or baseline visit.

19. Participants that are predisposed to the development of renal failure secondary to rhabdomyolysis (e.g. sepsis, hypotension, major surgery, trauma, severe metabolic, endocrine and electrolyte disorders; or uncontrolled seizures).
20. Participants with rare hereditary problems of galactose intolerance, the Lapp lactase deficiency or glucose-galactose-malabsorption.
21. Unwillingness or inability (e.g. physical or cognitive) to comply with study procedures (including study visits, fasting blood draws and compliance with study treatment regimens), and medication administration (injections) and schedule. Participant should be able and willing to read, understand and answer questionnaires.
22. Any surgical or medical condition, which in the opinion of the investigator, may place the participant at higher risk from his/her participation in the study, or is likely to prevent the participant from complying with the requirements of the study or completing the study at screening or baseline visit.
23. Use of other investigational drugs within 5 half-lives, 30 days or until the expected pharmacodynamic effect has returned to baseline (e.g. biologics), whichever is longer or longer if required by local regulation, prior to screening visit.
24. Pregnant or nursing (lactating) women at screening or baseline visit.
25. Women of child-bearing potential, defined as all women physiologically capable of becoming pregnant, unless they are using highly effective methods of contraception while taking study treatment, which includes rosuvastatin, and for 5 days (= 5 times the terminal half-life of rosuvastatin) after stopping medication. Highly effective contraception methods include:
 - Total abstinence (when this is in line with the preferred and usual lifestyle of the participant. Periodic abstinence (e.g. calendar, ovulation, symptothermal, post-ovulation methods) and withdrawal are not acceptable methods of contraception.
 - Female sterilization (have had surgical bilateral oophorectomy with or without hysterectomy), total hysterectomy, or bilateral tubal ligation at least six weeks before taking study treatment. In case of oophorectomy alone, only when the reproductive status of the woman has been confirmed by follow up hormone level assessment.
 - Male sterilization (at least 6 months prior to screening). For female participants on the study, the vasectomized male partner should be the sole partner for that participant.
 - Use of oral, (estrogen and progesterone), injected, or implanted hormonal methods of contraception or placement of an intrauterine device (IUD) or intrauterine system (IUS), or other forms of hormonal contraception that have comparable efficacy (failure rate < 1%), for example hormone vaginal ring or transdermal hormone contraception.

In case of use of oral contraception women should have been stable on the same pill for a minimum of 3 months before taking study treatment.

Women are considered post-menopausal if they have had 12 months of natural (spontaneous) amenorrhea with an appropriate clinical profile (e.g. age appropriate history of vasomotor symptoms). Women are considered not of child bearing potential if they are post-menopausal or have had surgical bilateral oophorectomy (with or without hysterectomy), total hysterectomy

or bilateral tubal ligation at least six weeks ago. In the case of oophorectomy alone, only when the reproductive status of the woman has been confirmed by follow up hormone level assessment is she considered not of child bearing potential.

If local regulations deviate from the contraception methods listed above to prevent pregnancy, local regulations apply and will be described in the local ICF.

6 Treatment

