5.1 Inclusion criteria

Participants eligible for inclusion in this study must meet **all** of the following criteria:

At Screening:

1. Written informed consent must be obtained before any assessment is performed.
2. Male or female participants ≥ 18 years of age.
3. Participants categorized as very high or high CV risk, as defined below:
 - **Very high risk participants** with at least one of the following:
 1. Documented ASCVD
 - ACS: Unstable angina or myocardial infarction
 - Stable angina
 - Coronary revascularization
 - Unequivocally documented ASCVD upon prior imaging
 - Stroke and Transient Ischaemic Attack (TIA)
 - PAD
 2. Diabetes mellitus (DM) with target organ damage (defined as microalbuminuria, retinopathy, or neuropathy), or at least ≥ 3 major risk factors, or early onset of Type 1 DM of long duration (> 20 years)
 3. A calculated SCORE2 $\geq 7.5\%$ for age < 50 years; SCORE2 $\geq 10\%$ for age 50-69 years; SCORE2-OP $\geq 15\%$ for age ≥ 70 years to estimate 10-year risk of fatal and non-fatal CVD

4. Pre-existing diagnosis of heterozygous familial hypercholesterolemia (HeFH) with ASCVD or with another major risk factor.

OR

- **High risk participants** with at least one of the following:
 1. Markedly elevated single risk factors, in particular total cholesterol > 310 mg/dL, LDL-C > 190 mg/dL, or blood pressure \geq 180/110 mmHg
 2. Pre-existing diagnosis of HeFH without other major risk factors
 3. DM without target organ damage (defined as microalbuminuria, retinopathy, or neuropathy), with DM duration \geq 10 years or other additional risk factor
 4. Moderate chronic kidney disease (eGFR 30-59 mL/min/1.73m²)
 5. A calculated SCORE2 2.5 to <7.5% for age under 50 years; SCORE2 5 to <10% for age 50-69 years; SCORE2-OP 7.5 to <15% for age \geq 70 years to estimate 10-year risk of fatal and non-fatal CVD

as defined by the cardiovascular risk categories in the 2019 ESC/EAS guideline ([Mach et al 2020](#)), [Note: Table 4, page 15: High risk and very high risk only] and updated SCORE2 and SCORE2-OP (according to [Hageman et al 2021](#), [de Vries et al 2021](#), [Visseren et al 2021](#)). Further details for documented ASCVD are provided in [Section 16.4](#).

4. LDL-C levels:
 - a. in participants with very high cardiovascular risk: serum LDL-C \geq 55 mg/dL.
 - b. in participants with high cardiovascular risk: serum LDL-C \geq 70 mg/dL

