6.6.1.1 Starting dose

Not applicable for blinded investigational treatment, inclisiran/placebo.

At the baseline visit (Day 1), all participants will be switched from their individual statin to open label study treatment, rosuvastatin. Participants can start rosuvastatin treatment either with 5 mg/day or 10 mg/day according to the local SmPC.

Start dose of 5 mg/day is recommended in patients:

- 70 years
- with moderate renal impairment (creatinine clearance < 60 mL/min)
- of Asian ancestry
- with predisposing factors to myopathy.

Considering the local SmPC, rosuvastatin starting dose will be chosen for a particular participant by the investigator. Participants already treated with rosuvastatin prior baseline visit will continue treatment with their individual MTD of rosuvastatin, if in accordance with the investigator.

Rosuvastatin should be used with caution in participants with pre-disposing factors for myopathy/rhabdomyolysis. Such factors include:

- renal impairment (severe renal impairment is an exclusion criterion ([Section 5.2](#)))
- hypothyroidism
- personal or family history of hereditary muscular disorders
- previous history muscular toxicity with another HMG-CoA reductase inhibitor or fibrate
- alcohol abuse
- age > 70 years
- situations where an increase in plasma levels may occur
- concomitant use of fibrates.

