
¹² Lp(a) will only be tested at screening, baseline, Day 90 and EOS. From this sample, triplicate serum aliquots will be made to allow Lp(a) testing in both nmol/L and mg/dL; a third aliquot will be made to allow testing of LDL-C and/or Lp(a) using novel methods currently in development.
 
¹³ A blood draw for PCSK9 levels will also be performed prior to participant switch to PCSK9 mAb, preferably once this switch is granted. The PCSK9 results will remain blinded and will not be used to influence treatment decisions. A plasma aliquot from the PCSK9 blood draw (e.g. SOMA) may also be used to profile proteins related to study drug or dyslipidemia.
 
¹⁴ AST, ALT, ALP, GGT, total bilirubin, CK, creatinine, creatinine clearance, eGFR, chloride, sodium, potassium, fasting glucose, HbA1C. Performed by the central lab.
 
¹⁵ ONLY: AST, ALT, ALP, GGT, CK, Total bilirubin. Performed by the central lab.
 
¹⁶ Hematocrit, Hemoglobin, Red Blood Cell (RBC) Count, Mean Corpuscular Volume (MCV), Mean Corpuscular Hemoglobin (MCH), Mean Corpuscular Hemoglobin Concentration (MCHC), Platelets, Erythrocyte Cell Morphology, White Blood Cell (WBC) count with Differential (Basophils, Eosinophils, Lymphocytes, Monocytes, Neutrophils, Bands). Performed by the central lab.
 
¹⁷ Urinalysis to include: specific gravity, pH, glucose, protein (total), ketones, bilirubin, urobilinogen, nitrite, hemoglobin (blood), leukocytes esterase. If dipstick measurement results are positive (abnormal), microscopic examination will be performed.
 
¹⁸ Done every day during the treatment period, using a digital hand-held device. Participant is to complete the diary everyday at home and the diary will be checked by the investigator at each site visit.
 
¹⁹ Training for each questionnaire should be completed with each participant prior to the first individual participant questionnaire completion.
 
²⁰ The Walking Impairment Questionnaire will only be completed by participants diagnosed with peripheral artery disease (PAD) at Baseline.
 
²¹ The Mac New Heart Disease Health Related Quality of Life Questionnaire will only be completed by participants diagnosed with Angina Pectoris (AP) at Baseline.
 
²² Theoretically, EOT and EOS happen on day 360, but if EOT occurs before the EOS visit, it is recommended that the participant remains in the study until the scheduled EOS. The assessments listed for this visit should only be conducted if the End of Treatment (EOT) and End of Study (EOS) occur simultaneously. An "early Exit" (premature discontinuation from study treatment and study on the same day before day 360) is considered as an EOS visit, and the assessments should be performed as they would be on EOS visit day 360. In case of premature treatment discontinuation, the assessments for the scheduled visit day should be performed (for details refer to Section 8.5.1 and Section 9.1.1).
																			

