Pregnancy Test	Serum / Urine pregnancy test (see Section 8.4.3)
Urinalysis	Dipstick measurements for: specific gravity, pH, glucose, protein (total), ketones, bilirubin, urobilinogen, nitrite, hemoglobin (blood), leukocytes esterase If dipstick measurement results are positive (abnormal), microscopic examination will be performed

*Reflex testing only in event of abnormal result from absolute count/ differentials

**eGFR will be calculated using the Modification of Diet in Renal Disease (MDRD) eGFR formula as follows:
 $175 \times [\text{standardized serum creatinine (mg/dL)}]^{-1.154} \times [\text{age}]^{-0.203} \times [1.212 \text{ if race=black/African American}] \times [0.742 \text{ if female}]$

***Diagnosis of diabetes based on HbA_{1c} \geq 6.5% (48 mmol/mol) or FPG two consecutive values \geq 126 mg/dL (7.0 mmol/L).

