10.2.2 Renal safety monitoring

For the open label study treatment (rosuvastatin) renal function should be monitored and assessments are outlined in the Assessment Schedule (Table 8-1). Rosuvastatin is contraindicated:

- in participants with severe renal impairment (creatinine clearance <30 mL/min) regardless of the dose,
- in participants with moderate renal impairment (creatinine clearance <60 mL/min) with 40 mg dose rosuvastatin.

Proteinuria, detected by dipstick testing and mostly tubular in origin, has been observed in patients treated with higher doses of rosuvastatin, in particular 40 mg, where it was transient or intermittent in most cases. Proteinuria has not been shown to be predictive of acute or progressive renal disease.

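### Severe renal impairment is measured by MDRD eGFR in the eligibility criteria but by creatinine clearance in the rosuvastatin contraindication, and the protocol treats the two as the same

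*Protocol*

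**What the plan says.** Protocol Section 5.2, criterion 12, excludes severe renal impairment, defined as eGFR below 30 mL/min/1.73m² "as calculated by the Modification in Diet in Renal Disease (MDRD) formula at screening or baseline visit". The equation is printed under Table 8-3 in Section 8.4.1.

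Section 10.2.2 states that rosuvastatin is contraindicated "in participants with severe renal impairment (creatinine clearance <30 mL/min) regardless of the dose". This uses the same clinical label with a different measure and different units.

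Section 6.6.1.1 lists predisposing factors that call for caution with rosuvastatin. One entry reads "renal impairment (severe renal impairment is an exclusion criterion", with a pointer to Section 5.2. The same section says: "At the baseline visit (Day 1), all participants will be switched from their individual statin to open label study treatment, rosuvastatin".

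Section 5.1 makes "Moderate chronic kidney disease (eGFR 30-59 mL/min/1.73m²" one of five alternative routes into the high-risk category, so participants just above the exclusion limit can qualify on renal function alone.

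Table 8-1, footnote 14, lists the central-lab chemistry panel as including "AST, ALT, ALP, GGT, total bilirubin, CK, creatinine, creatinine clearance, eGFR". Creatinine clearance and eGFR are therefore separate reported results. The panel is drawn at screening and at Day -10 where that visit takes place. No inclusion or exclusion criterion uses creatinine clearance, and the documents give no formula for it.

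**The concern.** The eligibility rule and the contraindication share a label but not a measure. MDRD eGFR is indexed to body surface area and takes no account of weight. Creatinine clearance is stated in plain mL/min and, on the usual estimate, falls with low weight and high age. The two can therefore disagree on one blood sample.

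A participant can satisfy criterion 12 and still meet Section 10.2.2's contraindication to the background drug assigned to everyone. The cross-reference in Section 6.6.1.1 makes this easy to miss, because it tells the site that severe impairment has already been screened out. The planned outputs would not show it either: SAP Table 5-2 labels severe renal impairment by eGFR alone.

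At stake are the safety of a small group and the consistency of the safety text. The primary comparison of inclisiran with placebo is not in question.

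**Working it through.** The plan states no figure to reproduce. The check asks whether the two limits can separate for realistic participants, and in which direction.

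**Inputs**
- Criterion 12: eGFR below 30 mL/min/1.73m² (Section 5.2).
- Contraindication: creatinine clearance below 30 mL/min (Section 10.2.2).
- eGFR = 175 × SCr^-1.154 × age^-0.203 × 0.742 if female (Section 8.4.1; the race factor is taken as 1 here).
- Creatinine clearance: Cockcroft-Gault, (140 − age) × kg / (72 × SCr) × 0.85 if female. This is an assumption.

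**One case in full.** Woman, 82 years, 55 kg, creatinine 1.5 mg/dL:
- eGFR = 175 × 0.6263 × 0.4088 × 0.742 = 33.2, so criterion 12 does not exclude her.
- Creatinine clearance = 58 × 55 / (72 × 1.5) × 0.85 = 25.1, so Section 10.2.2 contraindicates rosuvastatin.

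**Further cases**

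| Participant | SCr (mg/dL) | eGFR | CrCl (mL/min) |
|---|---|---|---|
| Woman, 80 y, 50 kg | 1.4 | 36.2 | 25.3 |
| Man, 80 y, 65 kg | 2.0 | 32.3 | 27.1 |
| Man, 82 y, 65 kg | 1.8 | 36.3 | 29.1 |
| Woman, 60 y, 85 kg | 1.7 | 30.7 | 47.2 |

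The last row shows no conflict: both values are above their limits, with creatinine clearance far above.

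**Weight below which the limits conflict.** Set creatinine clearance to 30 and solve: kg = 30 × 72 × SCr / ((140 − age) × 0.85 if female), where SCr is the value giving the stated eGFR.

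| Age, eGFR | Woman | Man |
|---|---|---|
| 80 y, eGFR 31 | 67.8 kg | 74.6 kg |
| 80 y, eGFR 35 | 61.0 kg | 67.2 kg |
| 80 y, eGFR 40 | 54.4 kg | 59.8 kg |
| 65 y, eGFR 31 | 56.3 kg | 61.9 kg |

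The window is widest in older, lighter people and mostly lies at eGFR of about 30 to 40. It can also reverse. At eGFR exactly 30, a woman of 50 years and 90 kg has a creatinine clearance of 53.5 mL/min, so someone like her just under the eGFR limit is excluded although well clear of the Section 10.2.2 limit.

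**Check without Cockcroft-Gault.** Removing the body-surface indexing from MDRD (Mosteller surface area) at 155 cm and 50 kg gives √(155 × 50 / 3600) = 1.467 m², and 30 × 1.467 / 1.73 = 25.4 mL/min. At 175 cm and 80 kg the same step gives 1.972 m² and 34.2 mL/min. The units alone separate the limits, in either direction.

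**The case against.** The strongest reply is that a site follows the whole protocol, not Section 5.2 in isolation. Section 10.2.2 itself states the contraindication, and Sections 3.4, 6.1.2, 6.6.1.1 and 10.2 defer repeatedly to the local SmPC. Exclusion 22 lets the investigator exclude anyone judged to be at higher risk. Inclusion 5 requires a contraindication check on the participant's current statin, which covers the roughly 10% who may enter already on rosuvastatin. Section 9.1.1 provides an alternative statin and continued escalation when rosuvastatin has to stop.

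All of this stands and limits the consequence. A reader might infer that the protocol directs sites to give rosuvastatin against its own contraindication, or that such participants fall out of the treatment strategy. The documents support neither. What remains is narrower. None of these provisions is a defined eligibility rule, inclusion 5 does not reach a drug newly started on Day 1, and Section 9.1.1 addresses stopping rosuvastatin rather than never starting it.

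A reader might also infer that rewording criterion 12 would keep such participants out. It would not: the Amendment 3 rationale records last participant first treatment on 26-Feb-2024 with 1776 randomized, so no enrolment decision remains.

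Finally, one could say that severe renal impairment is simply a single concept loosely worded, since SAP Section 5.4 labels it by eGFR and points to Protocol Section 10.2.2. That explains how the mismatch could arise but does not remove it, because the lab reports two separate values.

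**Conclusion.** The inconsistency is in the text and does not depend on any assumed formula: Sections 5.2 and 10.2.2 attach different measures to the same term, and Section 6.6.1.1 treats them as equivalent. Its practical size does depend on an assumption. With Cockcroft-Gault, the affected participants are older and lighter, with eGFR of about 30 to 40. A different creatinine-clearance method would move these boundaries. The documents give no baseline distribution of renal function, age or weight, so the number affected cannot be derived and may be very small.

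The documents do not show that anyone was exposed against the contraindication, nor do they settle which measure or limit should govern. This is a safety-text contradiction worth correcting because the data are already held. It does not threaten the trial's conclusions.

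**What to change.** 1. The sponsor should reconcile Sections 5.2, 6.6.1.1 and 10.2.2 so that severe renal impairment has one consistent meaning, and name the creatinine-clearance formula. The governing measure and limit are for the sponsor to decide.
2. Produce a one-off listing, from central-lab values already reported, of randomized participants whose baseline eGFR and creatinine clearance fall on different sides of the two stated limits. Send it to sites for review of those still on treatment or entering post-trial access (Section 6.1.4), and report it with the safety data.

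The second step is the one that can still act. On 2-Sep-2024, 1391 of the 1776 randomized had completed treatment, so at most 1776 − 1391 = 385 were still on treatment at that date, fewer if some had discontinued.

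The cost is one text clarification and one listing. No new tests are needed.

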6.1 Study treatment

Participants will be randomized 1:1 to double-blind s.c. injections of inclisiran sodium 300 mg or placebo. Investigational and control drugs will not be dispensed to the participants but administered by qualified, delegated healthcare personnel at the study site on Day 1, Day 90 and Day 270 of the study.

The open label study treatment, rosuvastatin, will be delivered to the participants at randomization and next visits for daily intake, and participants will be asked to return all unused rosuvastatin treatment and its packaging at each study visit.

6.1.1 Investigational and control drugs

The sponsor will provide the following investigational and control drugs, refer to [Table 6-1](#).

Table 6-1 Investigational and control drug

Treatment Title	Inclisiran ¹	Placebo
Treatment Description	Inclisiran sodium 300 mg (equivalent to 284 mg inclisiran) in 1.5 mL	Placebo in 1.5 mL
Types	Drug	Drug
Dose Formulation	Solution for injection	Solution for injection
Unit Dose Strength(s)	Inclisiran sodium 300 mg (equivalent to 284 mg inclisiran) in 1.5 mL	Placebo in 1.5 mL
Dosage Level(s)	Inclisiran sodium 300 mg as 1 injection of 1.5 ml at each of the timepoints specified in Table 8-1	Placebo as injection in 1.5 ml at each of the timepoints specified in Table 8-1
Route of Administration	Subcutaneous injection	Subcutaneous injection
Use	Experimental	Experimental
IMP	Yes	Yes
Sourcing	Provided centrally by the Sponsor (global)	Provided centrally by the Sponsor (global)
Packaging and Labeling	Study treatment will be provided in pre-filled syringes. Each syringe will be labeled as required per country requirement.	Study treatment will be provided in pre-filled syringes. Each syringe will be labeled as required per country requirement.
1 Inclisiran is also referred to as KJX839		

During the treatment period, a participant can become eligible for PCSK9 mAb treatment. Please refer to [Section 3.4](#) for decision on eligibility.

If, during the course of the study, as per assessment by the Steering Committee, a participant's condition warrants the use of a PCSK9 mAb, preferably **CCI** the participant will need to discontinue the blinded investigational treatment, inclisiran/placebo, but will remain in the study and will be followed-up until the participant's end of study.

In cases where the Steering Committee deems a participant not eligible for PCSK9 mAb and the Investigator decides to treat the participant as per local standard of care, the participant will need to discontinue study medication (inclisiran/placebo), but will remain in the study and will be followed-up until the participant's end of study.

For intractable cases with LDL-C still too high after LLT escalation (refer to [Section 3.4](#)), the Investigator can decide to have the participant discontinue study treatment (inclisiran/placebo) and to be treated as per local standard of care, e.g. considering LDL-apheresis as 'ultima ratio'. The participant will remain in the study and will be followed-up until the participant's end of study.

